The primary hypothesis is that not all patients will be ventilated according to the recommended LPV strategy. We further hypothesize that patient height will be a major predictor in determining compliance to LPV, as our clinical experience suggests that while IBW used to set tidal volumes is calculated based on height, many anesthesiologists set tidal volumes by actual weight rather than IBW. Therefore, this practice may result in tidal volumes outside of a patient's acceptable tidal volume as would be recommended by LPV guidelines. Our other hypothesized predictors to LPV compliance include predictors that indicate respiratory dysfunction (e.g. severe COPD, CHF) or severe illness (American Society of Anesthesiologists [ASA] classification, sepsis), as anesthesiologists may be more cognizant of the need for LPV in these patients. Lastly, we hypothesize that the COVID pandemic will introduce a shift towards increased LPV compliance, but this shift may not be sustained in the post-pandemic era as precautions waned.

5. Methods

Study design

Our study is a retrospective cohort study investigating the correlation between hypothesized predictors of LPV compliance and actual LPV practice in a large multi-center health authority. The study population is all patients who underwent a general anesthetic for any procedure at a Fraser Health Authority hospital from January 2014 – December 2023. See Section 7 for more details regarding inclusion and exclusion criteria.

Sampling and sample description

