We aim to use convenience sampling by including all patients who meet eligibility criteria. All procedures conducted under general anesthesia within the Fraser Health Authority with an endotracheal tube for over 30 minutes and within the date range specified that meet the inclusion criteria are eligible for inclusion in this study. This is a multicentre study and includes all hospitals within the Fraser Health Authority using Centricity Perioperative Anesthesia (CPA) system, which collects intraoperative data. The American College of Surgeons National Surgical Quality Improvement Program (NSQIP) is an outcomes-based program to measure and improve the quality of surgical care by tracking patient data preoperatively through 30-days postoperatively; NSQIP data will be used for perioperative variables such as comorbidities. Procedures must be followed by NSQIP and currently within the CPA database to be included in our study (see inclusion and exclusion criteria). Based on historical data and the surgical volume contributing to the Fraser Health CPA system we expect there to be approximately 100,000 cases.

Inclusion and exclusion criteria

Inclusion criteria for this retrospective study include any patient that is over the age of 18 and underwent general anesthesia with endotracheal tube placement for a procedure lasting ≥ 30 minutes. Patients must be included in the NSQIP database and linked to their anesthetic dataset within CPA by either their name, date of birth, medical record number (MRN, i.e. RC number), Personal Health Number (PHN), and/or date of surgery. Exclusion criteria for this retrospective study include: any patient that underwent cardiac or thoracic surgery or received an anesthetic that did not utilize an endotracheal tube, ASA 6 (organ donor), Hyperthermic intraperitoneal chemotherapy, transplant cases, surgical procedure related to an occurrence or complication of prior procedure during the same admission/within 30 days, multiple National Surgical Quality Improvement Program (NSQIP) assessed cases within 30 days only for same patient, cases in CPA that are unable to be linked to NSQIP data or vice versa.

6. Data collection

Data sources

Predictors and demographic data: The American College of Surgeons National Surgical Quality Improvement Program is a validated, risk adjusted, outcome-based program that measures the

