$$\text{Ideal body weight (IBW) (men)} = 50 \text{ kg} + 2.3 \text{ kg} \times (\text{height (inches)} - 60)$$

$$\text{Ideal body weight (IBW) (women)} = 45.5 \text{ kg} + 2.3 \text{ kg} \times (\text{height (inches)} - 60)$$

7. Statistical plan

Software

Microsoft Excel (Microsoft Corporation, Redmond, WA), R Console (R Foundation for Statistical Computing, Vienna, Austria), Anaconda Navigator Distribution (python), and SAS Base 9.4 statistical analysis software will be used for analysis.

Part I: Patterns of compliance to LPV and relationship with default ventilator settings

- Descriptive statistics for proportion compliance to LPV will be calculated for the entire dataset
- Among the non-compliance cases, the % attributable to the following will be calculated. This analysis is useful for determining areas of intervention/education required:
 - Low PEEP
 - Inappropriate (both too high or too low) tidal volume
 - Too low tidal volume
 - Too high tidal volume
 - Both low PEEP and inappropriate tidal volume
- Using the entire data set, for tidal volumes from 400-600mL, we will plot the % of patients in whom that tidal volume satisfies LPV criteria. This will inform any required change to the default tidal volume ventilator setting to maximize the number of patients satisfying LPV criteria if the tidal volume setting were left unchanged.
- We will model improvements in LPV compliance if the default PEEP setting on anesthesia machines were changed from PEEP = off to PEEP = 5.

Part II: Investigation of time trends to compliance

A Shewhart control chart (p chart) of LPV compliance each month will be presented to investigate time trends of LPV compliance as correlated to the COVID pandemic, and to identify special-cause variation in LPV compliance throughout the pandemic. The following rules to look for trends and shifts will be employed (5):

- 1 point is outside the control limits.
- 2 out of 3 consecutive points are more than 2 sigmas from the center line in the same direction.
- 4 out of 5 consecutive points are more than 1 sigma from the center line in the same direction.
- 8/9 points on the same side of the center line.
- 6 consecutive points are steadily increasing or decreasing.
- 14 consecutive points are alternating up and down.
- 15 consecutive points are within 1 sigma of the center line.
- 8 consecutive points on either side of the center line with not within 1 sigma.

Part III: Predictors of compliance to LPV

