- We will use a multivariate logistic regression model to determine the independent predictors of LPV use. Predictors with a $p < 0.2$ in the bivariate analysis will be incorporated into model construction. A conservatively high cut-off for the p-value was chosen to minimize type II error (exclusion of a predictor that would have become significant if adjusted for other predictors in the multivariate model). For the same reason, we will not adjust the p-value for multiple comparisons during the predictor screening phase.
- For face validity, we will include age, sex, height, obesity status, night or weekend shift, hospital site, laparoscopic surgery, and pre-COVID era vs. COVID era in the model regardless of bivariate analysis results.
- We will add candidate predictors that passed the bivariate phase in a forward selection method, minimizing the Akaike Information Criterion (3), which rewards improved goodness of fit while simultaneously penalizes over-fitting.
- Pairwise interaction among included terms will be investigated via adding an interaction term for each pair, and comparing the model with and without the interaction term via a likelihood ratio test. A $p < 0.05$ will result in inclusion of that interaction term. As before, to minimize type II error, the p value will not be adjusted for multiple comparison at this stage.
- Finally, the odds ratio of each predictor for LPV use in the final model will be presented with and without Bon Ferroni adjustment for multiple comparisons. A separate result will be presented for interactions, if any are detected.

Sensitivity analyses, subgroup analyses, and other supplemental analyses

- Part I: none planned
- Part II:
 - Subgroup analysis for: academic hospital sites, laparoscopic surgery.
 - Subgroup analysis for patients who would not have met LPV criteria if ventilated by default ventilator settings for tidal volume. This analysis explores whether clinicians became more likely to adjust the ventilator settings intentionally to achieve LPV.
- Part III:
 - We will adjust the date cut-offs for pre-COVID era vs. COVID era based on Shewhart chart results of Part II (i.e. the dates that the Shewhart chart indicated shifts in practice pattern)
 - Subgroup analysis for academic hospital sites only.

8. Ethical considerations

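### Part I's failure breakdown and PEEP-default projection have no period split, so they may not describe the practice that education and default changes would now address

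*Combined protocol and SAP*

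**What the plan says.** The cohort covers "any procedure at a Fraser Health Authority hospital from January 2014 – December 2023" (Section 5, Study design). A case must be in both databases: "Procedures must be followed by NSQIP and currently within the CPA database to be included in our study" (Section 5, Sampling and sample description). On size, the same section says "we expect there to be approximately 100,000 cases". That is a projection from past volume, without yearly counts or site start dates.

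Three outputs of Section 7, Part I, bear on this point:

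- Compliance rate: "Descriptive statistics for proportion compliance to LPV will be calculated for the entire dataset".
- Failure breakdown: "Among the non-compliance cases, the % attributable to the following will be calculated". The causes listed are low PEEP, tidal volume too high, too low or either, and both faults together. The plan says the breakdown will show where intervention or education is needed.
- PEEP-default projection: "We will model improvements in LPV compliance if the default PEEP setting on anesthesia machines were changed from PEEP = off to PEEP = 5".

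Only the first of these names the whole dataset. For the other two, pooling is inferred from the absence of any period and from the list of supplemental analyses at the end of Section 7, which reads "Part I: none planned".

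On change over time, Section 4 says "we hypothesize that the COVID pandemic will introduce a shift towards increased LPV compliance". The same sentence allows that the shift may not last into the post-pandemic period. Section 2 reports from cited work that non-protective ventilation has become less common but is still frequent.

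**The concern.** The breakdown and the projection look forward. One is to direct education; the other asks what a changed machine default would gain. Both need the failure pattern at the time of the change, but as written they average over ten years in which the plan itself expects practice to have moved.

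If PEEP use rose and stayed up, a pooled projection would overstate what a new default would now add. The pooled breakdown could also rank low PEEP as the leading fault after tidal volume had overtaken it. If practice moved and moved back, little would be lost. The plan as written could not tell these cases apart at the level of failure type.

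**Working it through.** **No figure in the plan to reproduce.** The expected 100,000 cases come with no annual volumes, so neither that total nor the yearly split can be rebuilt.

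**Share of the window.** January 2014 to December 2023 is 120 months. With the era limits in Section 7, Part III:

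- before January 2020: 72/120 = 60%
- January to June 2020: 6/120 = 5%
- July 2020 to December 2023: 42/120 = 35%
- January 2022 to December 2023: 24/120 = 20%

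These are shares of calendar time. If case volume grew by a constant percentage each year, the pre-2020 share of cases would be 54% at 5% growth and 48% at 10%, crossing one half at about 8.6%. With even accrual but linked data starting in 2016 it would be 4/8 = 50%; starting in 2017, 3/7 = 43%.

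**What Parts II and III add.** Part II charts monthly composite compliance. Part III models the same composite with an era term. A composite rate cannot be split afterwards. Let P be the proportion with adequate PEEP and V the proportion with adequate tidal volume, taken as independent. Compliance is P × V, and the most a PEEP default could add is V × (1 − P), if every low-PEEP case were corrected and tidal volumes did not change. Compliance of 30% can then arise from P = 50%, V = 60% (gain 0.60 × 0.50 = 30 points) or from P = 75%, V = 40% (gain 0.40 × 0.25 = 10 points).

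**Size of the distortion.** The documents give no component rates, so every P and V below is assumed. The periods are 2014–19, 2020–21 and 2022–23, with weights 0.6, 0.2 and 0.2 (even accrual).

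| Assumed trend | P (%) | V (%) | Pooled gain | 2022–23 gain | Difference |
|---|---|---|---|---|---|
| Stable | constant | constant | same | same | 0 |
| Partial reversion | 30/50/35 | 60 | 39.0 | 39.0 | 0 |
| Full reversion | 30/50/30 | 60 | 39.6 | 42.0 | −2.4 |
| Mild rise | 40/45/50 | 60 | 34.2 | 30.0 | +4.2 |
| Steep rise | 30/50/75 | 55/60/65 | 32.4 | 16.3 | +16.1 |

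Pooled gains, as proportions:

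- Partial reversion: 0.60 × (0.6 × 0.70 + 0.2 × 0.50 + 0.2 × 0.65) = 0.390.
- Full reversion: 0.60 × (0.6 × 0.70 + 0.2 × 0.50 + 0.2 × 0.70) = 0.396.
- Mild rise: 0.60 × (0.6 × 0.60 + 0.2 × 0.55 + 0.2 × 0.50) = 0.342.
- Steep rise: 0.6 × 0.385 + 0.2 × 0.300 + 0.2 × 0.1625 = 0.3235.

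**Failure mix under the steep rise.** Pooled compliance is 0.6 × 0.165 + 0.2 × 0.300 + 0.2 × 0.4875 = 0.2565, so 0.7435 fail. Low PEEP is present in 0.6 × 0.70 + 0.2 × 0.50 + 0.2 × 0.25 = 0.57 of cases, which is 0.57/0.7435 = 77% of failures. In 2022–23 alone, 0.5125 fail. Low PEEP is present in 0.25/0.5125 = 49% of them and a wrong tidal volume in 0.35/0.5125 = 68%, so the leading fault changes.

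**If linked data began in 2017** (weights 3/7, 2/7, 2/7), the steep rates give a pooled gain of 0.385 × 3/7 + 0.300 × 2/7 + 0.1625 × 2/7 = 29.7 points, against 16.3 in 2022–23. The gap does not need a pre-2020 majority.

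**The case against.** The strongest reply is that a decade-wide proportion correctly describes the stated population and answers Objective 1, which does not restrict itself to current practice. Current overall compliance will also be visible: Part II charts it every month to December 2023, and Part III forces an era term into the model. All of this stands, and the pooled rate should not be treated as a defect.

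The plan's hypothesis also includes fading of the pandemic effect, and the falling trend in Section 2 comes from cited literature, mostly from outside Canada. The distortion may therefore be nil. This stands too, and is why the table includes reversion.

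A reader might infer that Part I will mostly describe 2014–2019 practice, or that the decade average describes no current practice. The documents support neither. The 60% is calendar time, no yearly case counts are given, and modest growth or late linkage would bring the share of cases below half. Stable practice would make the average current.

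Part II also plans a subgroup of patients whom the default tidal volume would not have served, to see whether clinicians became readier to adjust settings. That touches on tidal volume, but it still follows composite compliance and gives neither the failure mix nor the PEEP gain by period.

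**Conclusion.** The concern holds for the failure breakdown and the PEEP-default projection. Neither has a period split, and nothing elsewhere in the plan recovers the current failure mix or the current PEEP gain. It does not extend to the pooled compliance rate. The tidal-volume plot depends on height and sex rather than on practice, so it is little affected.

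The size is unknown in advance. On assumed rates, the pooled PEEP gain is undistorted if practice is stable and differs little if practice reverts (zero or 2.4 points too low in the two cases shown). It is about 4 points too high under a mild rise and about 16 points too high under a steep one. These figures rest on even accrual, independent components and full correction of low PEEP by the default. This is a gap in reporting and targeting, not an error in any estimate.

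**What to change.** Keep the pooled compliance rate as the answer to Objective 1. Add to Part I the failure breakdown and the PEEP-default projection by calendar year or by the plan's eras. State that conclusions about education and default settings will be drawn from the most recent period, and define that period before the data are seen (for example, January 2022 to December 2023). Calendar year is the more informative split, because the single era after June 2020 would itself average over any fading. State also which cases enter the breakdown and the projection.

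The cost is SAP wording and a few tables. Date of surgery is already extracted (Section 6). Since Section 9 deletes it after linkage, year and month should be derived first, as the Part II chart already requires.

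Intervals widen slightly. Assuming even accrual and independent cases, 24 months hold about 20,000 cases, and the 95% half-width at 50% is 1.96 × √(0.25/20,000) = ±0.7 points. The breakdown has only failures in its denominator: at 50% compliance, about 10,000 failures give ±1.0 point. A single year would have about 10,000 cases (±1.0) and 5,000 failures (±1.4).

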For the past two decades, adoption of a similar strategy of ventilation in the intensive care unit for patients with acute respiratory distress syndrome have yielded decreased mortality (8-10). However, uptake of LPV usage in the operating room has been slower, with less than 50% compliance (11, 12). Factors that influence compliance in some centers include extremes of patient IBW, unoptimized default ventilator settings, and clinician misconceptions surrounding LPV guidelines (12-14). While adherence to LPV was higher for COVID positive patients during the start of the COVID pandemic with evidence for lower mortality in the intensive care unit (15, 16), it is unknown whether an increase in overall LPV compliance occurred outside of COVID positive patients, and if so, whether such a shift in practice was sustained. In addition, most studies querying LPV compliance occurred in centers outside of Canada (12-14), with differences in medical education and practice patterns compared to Canadian centers. To fill these gaps in the literature, we therefore aim to explore patterns of LPV compliance in a large Canadian health authority in a retrospective manner, and to elucidate predictors influencing LPV compliance. We will also explore trends of LPV compliance throughout the COVID pandemic, into the post-pandemic era.

2. Purpose and Justification

The purpose of this study is to investigate patterns of LPV compliance, elucidate predictors of LPV compliance, and gauge the effects of COVID on LPV compliance in Fraser Health Authority. Although the use of nonprotective ventilation has decreased over time, a large proportion of patients continue to be ventilated with high tidal volumes and little PEEP(13, 17, 18). While the use of LPV strategies has been improved, patients that are short-stature, obese, or female have an increased tendency to be ventilated with larger tidal volumes in non-Canadian studies (11, 19). Contributing to this shortfall may be lack of patient height documentation as well as lack of awareness by providers regarding the significant impact of height (rather than patient weight) in determining LPV ventilation parameters. Compliance with LPV has been shown to be increased following implementing education about LPV, feedback regarding developmental performance, departmental LPV policies, and modification of default ventilator

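### The monthly p chart in Part II allows for binomial variation only, so if compliance also varies from month to month by about 1 point SD or more, ordinary variation may be flagged as special cause

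*Combined protocol and SAP*

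**What the plan says.** Section 7, Part II: "A Shewhart control chart (p chart) of LPV compliance each month will be presented". One stated purpose is "to identify special-cause variation in LPV compliance throughout the pandemic". Eight signal rules follow. The first is "1 point is outside the control limits"; another is "2 out of 3 consecutive points are more than 2 sigmas from the center line in the same direction". Further rules use the 1-sigma zone, and others (a run on one side, a steady rise or fall, alternation) do not use sigma at all.

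The section gives no formula for sigma, no baseline period for the centre line, no overdispersion check and no alternative limits.

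Section 5 gives the volume, "we expect there to be approximately 100,000 cases", and the period, "from January 2014 – December 2023". It also says: "This is a multicentre study and includes all hospitals within the Fraser Health Authority using Centricity Perioperative Anesthesia (CPA) system".

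The chart is used in two places. It addresses the time-trend questions, which section 3 lists as secondary. Its signals also supply alternative era cut-off dates for a Part III sensitivity analysis. The main Part III era variable has fixed calendar cut-offs (before January 2020, after June 2020) and is kept in the model whatever the bivariate screen shows.

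**The concern.** Binomial limits are right if, in a stable period, monthly compliance differs only by sampling of cases. With several hundred cases a month that sampling error is small, so modest real variation between months becomes visible against it.

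The Part III predictor list shows that the investigators expect compliance to depend on site, specialty, shift, urgency, laparoscopy and patient factors. If the monthly mix of these moves, or if something shared affects a whole month, the monthly rate varies more than binomially without any special cause. As an illustration with assumed figures, take two case types whose compliance differs by 20 points. A 5-point change in their share moves the monthly rate by 0.20 × 0.05 = 1 point, and a 10-point change moves it by 2 points.

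At stake is the reading of the chart for the pandemic, when case mix could well have moved, and the choice of dates for the sensitivity analysis.

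**Working it through.** **Inputs.** From the documents: about 100,000 cases; January 2014 to December 2023, which is 10 × 12 = 120 months. Assumed: 3-sigma limits (the usual convention; the plan does not write them out), equal monthly volume, independent normal month effects, and compliance p of 20% to 50%. No local rate is given; the background text before section 2 reports operating-room uptake "with less than 50% compliance". The extra between-month SD, tau, is not in the documents, so a range is shown. The plan states no control limit or false-signal rate that could be reproduced.

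**Monthly count.** 100,000 / 120 = 833.

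**Binomial sigma**, sqrt(p(1 − p)/833):
- p = 0.2: 1.39 points, limits ±4.2
- p = 0.3: 1.59 points, limits ±4.8
- p = 0.5: 1.73 points, limits ±5.2

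**Effect of extra variation.** The variance ratio is phi = 1 + tau²/sigma². The chance that a stable month falls outside 3 sigma is 2 × (1 − Φ(3/√phi)); multiplying by 120 gives the expected number of months. At p = 0.3:

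| tau (points) | phi | 3/√phi | Months outside, of 120 | Chance of at least one |
|---|---|---|---|---|
| 0 | 1.00 | 3.00 | 0.32 | 28% |
| 0.5 | 1.10 | 2.86 | 0.51 | 40% |
| 1 | 1.40 | 2.54 | 1.34 | 74% |
| 1.5 | 1.89 | 2.18 | 3.51 | 97% |
| 2 | 2.59 | 1.87 | 7.46 | about 100% |

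Simulation with the centre line estimated from the same 120 months gives nearly the same counts: 0.3, 0.5, 1.3, 3.4 and 7.2 to 7.3. At tau = 2 points the formula gives 10.5 months for p = 0.2 and 5.9 for p = 0.5.

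**Other rules** (simulation, p = 0.3, share of stable charts with at least one signal):

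| Rule | tau 0 | tau 1 | tau 2 |
|---|---|---|---|
| 2 of 3 beyond 2 sigma | 19% | 56% | 99% |
| 4 of 5 beyond 1 sigma | 30% | 56% | 91–92% |
| Nine on one side | 17–18% | 17–18% | 17–18% |

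**With Laney p' limits.** Let z be the standardised monthly values and sigma-z the mean absolute difference of successive z divided by 1.128. Multiplying the binomial sigma by sigma-z returns the number outside 3 sigma to about 0.3 of 120 at every tau examined. The chance of at least one is 25–29%, or about 31% if sigma-z comes from the 72 pre-COVID months (2014 to 2019, 6 × 12). The 2-of-3 and 4-of-5 rules return to, or close to, their rates at tau = 0.

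**Detection of a real shift.** The case checked is a sustained 3-point rise with pre-COVID baseline, p' limits and tau = 2 points. The 3-sigma rule alone signals in about 74% of series over the 42 months from July 2020 to December 2023 (6 + 36). Adding nine on one side raises this to about 98%.

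**All eight rules together** (one-side run read as nine points). With purely binomial data, about 77% of 120-month charts show at least one signal, with about 2.5 flagged months. With p' limits the share stays at about 77% at each tau examined.

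**The case against.** A reader might infer that ordinary variation will be flagged, or that the limits are simply too narrow. The documents do not support that. They give neither a between-month SD nor a local compliance rate. Limits of ±4 to 5 points are not extreme, and an extra SD of 0.5 point adds almost nothing (0.5 against 0.3 months). Stable differences between hospitals, clinicians or patients do not by themselves widen month-to-month variance; a moving mix or shared monthly influences are needed, and the plan does not quantify either. This stands, so the point is conditional.

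A reader might also infer that the chart decides whether practice changed. It does not do so alone. The main era contrast uses fixed dates in an adjusted model, and chart dates enter a sensitivity analysis only. A single month beyond 3 sigma is not naturally read as a shift, and the nine-on-one-side rule is insensitive to limit width. This also stands, but only in part: the 2-of-3 and 4-of-5 rules are among those the plan uses to look for trends and shifts, and they inflate.

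Finally, p' limits leave about 77% of stable charts with some signal when all eight rules are applied, and they reduce the power of the 3-sigma rule. Both are true. The first is a separate problem; the second is the price of valid limits. On a binomial chart at tau = 2 points (p = 0.3), about 17 months are flagged under the eight rules instead of about 2.5, so the width of the limits matters in its own right.

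**Conclusion.** The concern holds conditionally. A monthly p chart with 833 cases per point carries a sigma of 1.4 to 1.7 points and no allowance for other month-to-month variation. If that variation has an SD of roughly 1 point or more, the 3-sigma, 2-of-3 and 4-of-5 rules may flag ordinary months as special cause: about one false 3-sigma month per chart at 1 point and about seven at 2 points, for 30% compliance. Below about 0.5 point the effect is negligible.

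The result rests on the assumed compliance range, equal monthly volumes and independent month effects. The consequence is limited to the secondary time-trend questions and one Part III sensitivity analysis. Since the size of the extra variation is unknown now but can be estimated from the data already planned, the check should be specified in advance.

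**What to change.** Add to section 7, Part II:

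- Take the centre line and sigma-z from the pre-COVID months (before January 2020), with sigma-z from the moving range of the standardised monthly values, and report sigma-z.
- Use Laney p' limits, p̄ ± 3 × sigma-z × sqrt(p̄(1 − p̄)/n) for each month's n, and scale the 1- and 2-sigma zones the same way.
- Apply this to the main chart and to each subgroup chart, with sigma-z estimated separately.

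The cost is small. It needs no new data, and the calculation can be done in the software already listed. When sigma-z is near 1 the chart is essentially the planned one.

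The downside is wider limits when overdispersion is present. At 2 points of extra SD and 30% compliance, sigma-z is about √2.59 = 1.61, so the limits widen from ±4.8 to about ±7.7 points (3 × 1.61 × 1.59). The 3-sigma rule alone then detects a sustained 3-point shift in about 74% of series; keeping the nine-on-one-side rule restores this to about 98%. The pre-COVID baseline matters: with all 120 months as baseline, detection at that SD fell to about 80%.

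This change does not address false signals from applying eight rules at once. Whether to use a smaller rule set should be decided separately.

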settings (12, 14, 19). Therefore, identifying patterns and predictors of LPV compliance in a Canadian context through our study may help inform the design of educational efforts and systemic changes to tackle areas of deficiency.

3. Research question

Primary research question: In patients undergoing general anesthesia with an endotracheal tube for non-cardiac surgery, what is the compliance rate to LPV in Fraser Health Authority, and predictors of such compliance?

Secondary research questions: What are time trends and shifts in LPV compliance from the pre-COVID to the post-COVID era? Are these trends sustained into the “new normal” era?

4. Research objectives and hypothesis

The objectives for this study are to:

1. Identify rates of compliance with LPV guidelines in the Fraser Health Authority in the Province of British Columbia, Canada. Compliance with ventilation guidelines is defined as meeting two criteria. The first is that their average tidal volume is 6-8 mL/kg IBW and the second is that the average positive end expiratory pressure (PEEP) is at least 5 cm H₂O. Patients ventilated according to one or neither of the above criteria will not be considered to have been ventilated according to the guidelines.
2. To elucidate predictors of compliance with LPV practice among providers. These predictors may help inform the design of educational efforts and systemic changes to tackle areas of deficiency.
3. To elucidate time trends and shifts in LPV compliance from the pre-COVID pandemic to post-pandemic era.
4. To evaluate whether time trends and shifts in LPV compliance through the pandemic are sustained.

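### Part II has no method that estimates a time trend in LPV compliance or separates gradual drift from a step, although objectives 3 and 4 need both

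*Combined protocol and SAP*

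**What the plan says.** Objective 3 (Section 4) is "To elucidate time trends and shifts in LPV compliance from the pre-COVID pandemic to post-pandemic era". Objective 4 asks whether those patterns last.

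The analysis for both is Section 7, Part II: "A Shewhart control chart (p chart) of LPV compliance each month will be presented to investigate time trends of LPV compliance". Eight rules follow, introduced by "The following rules to look for trends and shifts will be employed". One of them concerns sustained direction: "6 consecutive points are steadily increasing or decreasing". One concerns alternation. The other six concern distance from, or side of, the centre line, for example "8/9 points on the same side of the center line". No rule is labelled as a trend rule or a shift rule, and the months that set the centre line are not stated.

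Part III carries time only as a two-level era variable (before January 2020, after June 2020). Its sensitivity analyses add: "We will adjust the date cut-offs for pre-COVID era vs. COVID era based on Shewhart chart results of Part II". No slope, segmented model or calendar-time term appears anywhere in the plan.

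**The concern.** A p chart compares each month with a flat line. If compliance was already drifting upward before 2020, later months sit above that line with no pandemic effect at all. The plan has nothing that would show whether a signal came from drift or from a step.

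Three results are exposed. Under objective 3, drift could be described as a COVID-era shift. Under objective 4, that shift could look sustained, because a rising series does not return to a flat line. In Part III, dates produced by drift could become the revised era cut-offs in the sensitivity analysis.

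A pre-existing drift is plausible. Section 2 says of the published literature: "Although the use of nonprotective ventilation has decreased over time".

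**Working it through.** The plan gives no false-alarm rate, power or trend size for the chart, so there is no figure of its own to reproduce. The check simulates the chart, with up to 20,000 series per scenario.

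**Inputs**
- From the documents: January 2014 to December 2023 gives 10 × 12 = 120 monthly points. About 100,000 cases gives 100,000 / 120 = 833 a month.
- Assumed: even monthly volume, binomial variation, straight-line trends, and the baseline levels and trend sizes named below.

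**1. Drift against noise**
- A 20-point rise is 20 / 119 = 0.17 point a month.
- At 40% compliance the monthly SD is √(0.4 × 0.6 / 833) = 1.70 points, so drift is about 0.1 SD per step.
- The SD of a month-to-month difference is √(2 × 0.3 × 0.7 / 833) = 2.2 points at 30%, and 1.70 × √2 = 2.4 points at 40%.

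**2. The directional rule.** Six points means five moves. One window of six independent points is monotone with probability 2 / 6! = 0.28%, and 120 months contain 115 overlapping windows. Chance that the rule fires at least once:

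| Setting | Flat | 20-point rise |
|---|---|---|
| 833 a month | 17-18% | 23-24% |
| 833 a month, upward runs only | about 9% | 20-21% |
| 833 a month, 2 points extra monthly SD | 20% | 23% |
| 400 a month | 16.5% | 18-19% |
| 200 a month | 14% | 14-15% |

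**3. The level rules under slow drift.** Take a rise from 28% to 32% over the ten years with no COVID effect.
- Mean of months 1-72 (pre-COVID): 28 + 4 × 35.5 / 119 = 29.2%.
- Mean of months 79-120 (July 2020 onward): 28 + 4 × 98.5 / 119 = 31.3%.
- Difference: 2.1 points. Sigma is √(0.292 × 0.708 / 833) = 1.6 points, so later months sit on average about 1.3 sigma above the earlier line.
- Simulated chance of a point beyond 3 sigma or nine in a row on one side after June 2020: about 99.7% against a pre-COVID line (about 19% when flat), and 90% against an all-month line (15% when flat).

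**4. Where the signal falls.** Take a 20-point straight rise and an all-month centre line. The 3-sigma, two-of-three, four-of-five and same-side rules each fire in about 100% of charts, and about 59 of 120 months lie beyond 3 sigma. The first run of nine above the line starts at median month 71 (November 2019), with a 5th-95th percentile range of months 63-79 (March 2019 to July 2020). The line is crossed near mid-series, which happens to lie close to the era boundary.

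**5. A segmented regression on the same data.** This was tested as a linear model with a pre-COVID slope, level and slope changes from July 2020, and January-June 2020 left out.
- Straight trend, no COVID effect: false level change in 5-6%.
- Power for the 28% to 32% slope: 96% (88% with 1 point extra monthly SD).
- Power for a 3-point step on a 25% to 35% trend: 97-99.6%.
- Level and slope change tested separately: at least one falsely significant in 9-11%, hence a joint test.
- Flagging departures from the extrapolated pre-COVID line instead: false signals in about 33% of trend-only series.
- Curved 25% to 35% trend, no COVID effect: false level change in about 65% (levelling off) and in 74-93% (S-shaped, depending on the assumed shape).

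**The case against.** The strongest reply is that the chart does not miss a rise. Under a 20-point rise four of the plan's own rules fire almost surely, about half the months fall outside the limits, and the chart will be presented. That stands. A reader might infer that trends would go unseen, and the documents do not support that. What is missing is an estimate, and a way to tell drift from step.

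A reader might also infer that the plan would report a steady trend as a shift. That is a likely reading, not stated text: the rules are given jointly and none is tied to either word. Nor does the plan say it expects a secular trend. The Section 2 sentence summarises other studies, and Section 4 hypothesises a shift that may not last.

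The directional rule is not useless. It fires in 64% of series for 20 points gained over 12 months and 85% over 6 months. Its weakness is with slow change. Nor should it be read as six successive moves (seven points), for which the rates are 2.3% flat and 4.2% with the 20-point rise.

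The reach is limited as well. Part II serves secondary questions, the main Part III era variable has fixed and justified dates, and chart dates enter only one sensitivity analysis.

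Finally, a straight-line segmented model can itself create a false shift if the underlying trend is curved. That stands and shapes the fix.

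**Conclusion.** The point holds as a gap in Part II: no trend is estimated, and drift is not separated from a step. The directional rule hardly distinguishes a slow rise from none (17-18% against 23-24%; upward runs about 9% against 20-21%). The level rules respond to a drift of only 4 points in ten years almost as surely as they would to a real step (about 99.7% against about 19% when flat, on a pre-COVID line).

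These rates rest on assumed baselines, trend sizes, straight trends, even monthly volume and binomial variation. The contrast for the directional rule shrinks further at lower volume and disappears for steep ramps, which the rule does detect. The conclusion that the plan has no trend estimate rests on the text alone.

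The change should be made before analysis. It affects the secondary questions and one sensitivity analysis, not the main compliance estimate or the main Part III model.

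**What to change.** Keep the p chart and all its rules as the display. Add to Part II:

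1. A pre-specified segmented quasi-binomial regression of monthly compliance on calendar month, with a pre-COVID slope, level and slope changes from July 2020, January-June 2020 as its own step, and autocorrelation-robust standard errors. Report the slope and the level change with 95% CIs.
2. A joint test of level and slope change. Attribute a shift to the COVID era only when this test supports it, not from a chart signal and not from departures from an extrapolated pre-COVID line.
3. A pre-specified repeat with a smooth (spline) pre-existing trend. Claim a shift only if it holds in both models.
4. In the Part III sensitivity analysis, use chart dates only when the joint test supports a change.

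The cost is SAP wording and a few lines of code on data already planned. The downside is that the first model assumes a straight pre-COVID trend on the logit scale, and a curved trend can produce a false level change. The repeat in item 3 guards against that, and requiring both models to agree will give up some power.
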